4.6.3 Assessments during the Double-Blind Treatment Period

In the double-blind treatment period, participants will receive up to 49 (in scenario 1) or 55 (in scenario 2, if applicable) SC administrations of study drug over the course of 114 or 126 (if applicable) weeks, respectively. The final on-treatment efficacy and safety assessments are scheduled 2 weeks after the last dose. Participants who have completed the double-blind treatment period at the time of the implementation of *the study extension by 12 weeks*, received up to 43 doses and underwent the final efficacy and safety assessments at Week 104, 2 weeks after the last dose.

The same recommended order of clinical assessments and rating scales as above for the baseline visit should be followed (omitting those that are not conducted per the schedule of activities; see [Appendix 1](#)). *However, in exceptional circumstances, for post-randomization visits, if the caregiver, the primary rater or even the participant cannot perform these assessments as per schedule of activities, they may be performed up to 4 weeks out of window.*

Vital sign measurements, ECGs, blood draws for clinical laboratory assessments, PK, ADA, plasma biomarkers, and urine samples are *must be performed prior to study drug administration. They are also* recommended to be conducted following scale assessments.

If assessments are split over 2 days, all safety assessments must be done on same day as the treatment administration.

On each dosing day, after all assessments prior to dosing have been completed (see the schedule of activities in [Appendix 1](#)), gantenerumab or matching placebo will be administered subcutaneously at room temperature. For the first four doses, participants should be observed for a minimum of 2 hours after dosing and then for a minimum of 1 hour after all remaining doses (i.e., Doses 5 and beyond). Participants should leave the study center after injections only if they appear to be tolerating the injections. When doses are to be administered remotely from the clinical sites, study drug administration may be performed only by qualified health care providers, as defined by local regulations, who must remain with the participants for a minimum of 1 hour after each injection and be equipped with rescue medications.

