4.6.4 Assessments during Open-Label Extension Period

The same recommended order of clinical assessments and rating scales as in the double-blind treatment period (see [Appendix 1](#)), as well as vital sign measurements,

ECGs, blood draws for clinical laboratory assessments, PK, ADA, plasma biomarkers, and urine samples *must be performed prior to study drug administration*. They are also recommended to be conducted following scale assessments. If assessments are split over 2 days, all safety assessments must be performed on the same day as the treatment administration.

On each dosing day, after all assessments prior to dosing have been completed (see [Appendix 1](#)), gantenerumab and/or matching placebo will be administered subcutaneously at room temperature. For the first eight doses, participants should be observed for a minimum of 2 hours after dosing and then for a minimum of 1 hour after all remaining doses (i.e., doses 9 and beyond). Participants should leave the study center after injections only if they appear to be tolerating the injections. When doses are to be administered remotely from the clinical sites, study drug administration may be performed only by qualified health care providers, as defined by local regulations, who must remain with the participants for a minimum of 1 hour after each injection and be equipped with rescue medications.

Rescue medications to treat anaphylactic and anaphylactoid reactions must be available at the site or at the dosing location for HN visits. Participants and their study partners will be alerted to watch for signs of anaphylactic and anaphylactoid reactions and to contact the study center as soon as possible if any such signs are noted.

In the OLE, visits at which the participant receives study drug may take place ± 3 days of the protocol-specified date for Q2W administration per the schedule of activities in [Appendix 1](#). Always return to the initial planned schedule per randomization for subsequent visits.

For sites and participants for whom this is practical, visits that require only dosing, vital sign measurements, urine pregnancy test, C-SSRS assessment, and adverse event assessment may be performed at an alternate location conducted by appropriate health care professionals.

Refer to [Appendix 1, Table 3](#) for the schedule of activities during the OLE.

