- ^q Vital signs include measurements of pulse rate and systolic and diastolic blood pressure. Blood pressure and pulse rate should be taken when the participant is at rest and should not be measured unless at least 15 minutes have elapsed since the last blood draw. The same arm should be used for all blood pressure measurements. Pulse rate will be determined and will be recorded as beats per minute. If obtained manually, the pulse rate should be counted for a minimum of 20 seconds at each assessment.
- ^r Females of childbearing potential (including those who have had a tubal ligation) must have a urine pregnancy test performed at the site prior to each dose administration. If a urine pregnancy test is positive, it must be confirmed by a serum pregnancy test at the central laboratory. Results are to be recorded only in the source documents.
- ^s Study drug administration should be performed only after all assessments/rating scales for the participant are completed (unless indicated otherwise). Study drug will be administered to participants by SC injection. Participants should be observed up to 2 hours after dosing. After the fourth injection visit, the observation time may be reduced to 1 hour. Study personnel preparing and administering study drug must not be involved with any efficacy assessments or safety evaluations.
- ^t Height measured at screening only.
- ^u A plasma biomarker sample will be obtained as soon as is practical (e.g., at an unscheduled visit) once the site becomes aware of the occurrence or worsening of ARIA-E or of the occurrence of ARIA-H meeting discontinuation criteria.
- ^v A plasma PK sample will be obtained as soon as is practical (e.g., at an unscheduled visit) once the site becomes aware of the occurrence or worsening of ARIA-E or of the occurrence of ARIA-H meeting discontinuation criteria.

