Appendix 1: Schedule of Activities (cont.)

Table 2: Week 36 to the End of Study: 510 mg Q2W (cont.)

- ^k Lumbar puncture must be performed in the morning (between 8:00 a.m. and noon) to minimize potential diurnal variation of CSF parameters and should be performed prior to dosing. For participants enrolling based on CSF eligibility criteria, CSF and matching serum samples are optional at Week 76. Lumbar puncture does not have to be performed the same day as the main Week 76 visit or Week 104 visit, but should be performed in a reasonable time around these visits. The need for CSF collection at early termination visit will be discussed on a case-by-case *based on the participant's condition and the time since last lumbar puncture and advice by the Medical Monitor may be sought*.
- ^l Vital signs include measurements of pulse rate and systolic and diastolic blood pressure. Blood pressure and pulse rate should be taken when the participant is at rest and should not be measured unless at least 15 minutes have elapsed since the last blood draw. The same arm should be used for all blood pressure measurements. Pulse rate will be determined and will be recorded as beats per minute. If obtained manually, the pulse rate should be counted for a minimum of 20 seconds at each assessment.
- ^m Females of childbearing potential (including those who have had a tubal ligation) must have a urine pregnancy test performed at the site prior to each dose administration. If a urine pregnancy test is positive, it must be confirmed by a serum pregnancy test at the central laboratory. Results are to be recorded only in the source documents.
- ⁿ Study drug administration should be performed only after all assessments and rating scales for the participant are completed (unless indicated otherwise). Study drug will be administered to participants by subcutaneous injection (full details are provided in the pharmacy manual). Participants should be observed for up to 2 hours after dosing. After the fourth injection visit, this observation time may be reduced to 1 hour. Study personnel preparing and administering study drug must not be involved with any efficacy assessments or safety evaluations.
- ^o A plasma biomarker sample will be obtained as soon as is practical (e.g., at an unscheduled visit) once the site becomes aware of the occurrence or worsening of ARIA-E or of the occurrence of ARIA-H meeting discontinuation criteria.

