Appendix 1: Schedule of Activities (cont.)

Table 3: Scenario 1 / Week 104 to the End of Study: 510 mg Q2W (3-Month Extension)

puncture does not have to be performed the day of Week 76 or Week 116 visit, but should be performed in a reasonable time around these visits; the need of CSF collection at early termination visit *should be determined on a case-by-case basis based on the participant's condition and the time since last lumbar puncture and advice from the Medical Monitor* may be sought.

- ^l Vital signs include measurements of pulse rate and systolic and diastolic blood pressure. Blood pressure and pulse rate should be taken when the participant is at rest and should not be measured unless at least 15 minutes have elapsed since the last blood draw. The same arm should be used for all blood pressure measurements. Pulse rate will be determined and will be recorded as beats per minute. If obtained manually, the pulse rate should be counted for a minimum of 20 seconds at each assessment.
- ^m Females of childbearing potential (including those who have had a tubal ligation) must have a urine pregnancy test performed at the site prior to each dose administration. If a urine pregnancy test is positive, it must be confirmed by a serum pregnancy test at the central laboratory. Results are to be recorded only in the source documents.
- ⁿ Study drug administration should be performed only after all assessments and rating scales for the participant are completed (unless indicated otherwise). Study drug will be administered to participants by subcutaneous injection (full details are provided in the pharmacy manual). Participants should be observed for about 1 hour after dosing. Study personnel preparing and administering study drug must not be involved with any efficacy assessments or safety evaluations.
- ^o A plasma biomarker sample will be obtained as soon as is practical (e.g., at an unscheduled visit) once the site becomes aware of the occurrence or worsening of ARIA-E or of the occurrence of ARIA-H meeting discontinuation criteria

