- ^h MRI must be performed at least 7 days before dosing and results must be available for review by site staff before dosing can proceed. MRI should be performed before or at least 3 days following a lumbar puncture.
- ⁱ Vital signs include measurements of pulse rate and systolic and diastolic blood pressure. Blood pressure and pulse rate should be taken when the participant is at rest and should not be measured unless at least 15 minutes have elapsed since the last blood draw. The same arm should be used for all blood pressure measurements. Pulse rate will be determined and will be recorded as beats per minute. If obtained manually, the pulse rate should be counted for a minimum of 20 seconds at each assessment.
- ^j Females of childbearing potential (including those who have had a tubal ligation) must have a urine pregnancy test performed at the site prior to each dose administration. If a urine pregnancy test is positive, it must be confirmed by a serum pregnancy test at the central laboratory. Results are to be recorded only in the source documents.
- ^k Study drug administration should be performed only after all assessments and rating scales for the participant are completed (unless indicated otherwise). Study drug will be administered to participants by subcutaneous injection (full details are provided in the pharmacy manual). Participants should be observed for up to 2 hours after dosing. After the 8th injection visit, this observation time may be reduced to 1 hour. Study personnel preparing and administering study drug must not be involved with any efficacy assessments or safety evaluations.

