Appendix 1: Schedule of Activities (cont.)

Table 6: Schedule of Activities (OLE Week 24 to Week 35: Dose Escalation with Q2W Administration) (cont.)

- ^m Study drug administration should be performed only after all assessments and rating scales for the participant are completed (unless indicated otherwise). Study drug will be administered to participants by subcutaneous injection (full details are provided in the pharmacy manual). Participants should be observed for up to 2 hours after dosing. After the 8th injection visit, this observation time may be reduced to 1 hour. Study personnel preparing and administering study drug must not be involved with any efficacy assessments or safety evaluations.
- ⁿ A plasma biomarker sample will be obtained as soon as is practical (e.g., at an unscheduled visit) once the site becomes aware of the occurrence or worsening of ARIA-E or of the occurrence of ARIA-H meeting discontinuation criteria.

Appendix 2
National Institute on Aging/Alzheimer’s Association Criteria for Mild Alzheimer’s Disease

NIA/AA Category	Description

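### Two schedule footnotes turn the 2-hour minimum post-dose observation for the early injections into 'up to 2 hours', with no minimum stated

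*Protocol*

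**What the plan says.** For the double-blind period, Protocol Section 4.6.3 states: "For the first four doses, participants should be observed for a minimum of 2 hours after dosing". From dose 5 onward the floor drops to 1 hour. The same section adds a release condition: "Participants should leave the study center after injections only if they appear to be tolerating the injections".

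For the OLE, Section 4.6.4 has the parallel rule: "For the first eight doses, participants should be observed for a minimum of 2 hours after dosing". From dose 9 onward the floor is again 1 hour.

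The schedule of activities in Appendix 1 words this differently, in footnotes attached to the study drug administration row:

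- Table 1, footnote s (double-blind doses 1 to 9): "Participants should be observed up to 2 hours after dosing. After the fourth injection visit, the observation time may be reduced to 1 hour".
- Table 5, footnote k (OLE doses 1 to 12): "Participants should be observed for up to 2 hours after dosing. After the 8th injection visit, this observation time may be reduced to 1 hour".
- Table 2, footnote n, and Table 6, footnote m, repeat the 'up to' wording, ending "After the fourth injection visit, this observation time may be reduced to 1 hour" and "After the 8th injection visit, this observation time may be reduced to 1 hour" respectively.
- Table 3, footnote n, and Table 4, footnote n: "Participants should be observed for about 1 hour after dosing".

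**The concern.** A minimum is a floor and 'up to' is a ceiling. For the early injections the body gives the first and the footnotes give the second. Taken literally, the two agree only at exactly 2 hours.

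Site staff may well work from the footnote. Section 4.6.3 sends the reader to Appendix 1 for treatment-period activities, and the footnote hangs on the dosing row itself. The instruction is a safety one: it sits beside the requirement to have rescue medication available for anaphylactic reactions, and Section 5.1.1.3 recognises that anti-drug antibodies could lead to allergic reactions, including anaphylaxis, while rating the immunogenic risk as low. Section 9.2 asks investigators to document deviations, yet the same observation time can be a deviation under the body and compliant under the footnote.

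**Working it through.** There is no planned figure to reproduce. The check sets each footnote against the body text for the doses its table covers.

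| Doses | Body text | Footnote | Conflict in practice? |
|---|---|---|---|
| Double-blind 1–4 (Table 1, s) | at least 2 h | up to 2 h | Yes |
| Double-blind 5–9 (Table 1, s) | at least 1 h | may be reduced to 1 h | No |
| Double-blind 10–43 (Table 2, n) | at least 1 h | up to 2 h, then 1 h after visit 4 | No; the table starts after the step-down |
| Double-blind 44 onward (Tables 3 and 4, n) | at least 1 h | about 1 h | Wording only |
| OLE 1–8 (Table 5, k) | at least 2 h | up to 2 h | Yes |
| OLE 9–12 (Table 5, k) | at least 1 h | may be reduced to 1 h | No |
| OLE 13–18 (Table 6, m) | at least 1 h | up to 2 h, then 1 h after visit 8 | No; the table starts after the step-down |

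**Share of doses affected.**

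- Double-blind: Section 4.6.3 gives up to 49 doses in scenario 1, the scenario that applies because SAP Section 1.2 says the further 12-week extension was not implemented. 4 / 49 = 8.2%.
- OLE: Tables 5 and 6 number the doses 1 to 18. 8 / 18 = 44.4%.

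**Size of the gap.** Read alone, 'up to 2 hours' sets no lower limit. Read with the next sentence, it implies more than 1 hour before the step-down, because a later reduction to 1 hour presupposes a longer period. The shortfall on that reading is 2 h minus something above 1 h, so less than 1 hour. A 90-minute observation after dose 2, for example, fits the footnote and is 30 minutes short of the body's floor.

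**Could remote dosing explain the difference?** No. Section 4.6.3 gives remote providers a 1-hour minimum, but Table 1 marks home administration only from dose 5 and Table 5 only from OLE dose 9. All the affected doses are site visits on the schedule.

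**Is the OLE count right?** Section 4.3.2.2 defines an OLE dose, for uptitration, as two consecutive dosing visits. For observation, per-visit counting fits better: Table 5 numbers each visit as a dose, footnote k counts injection visits, and both match the eight in Section 4.6.4. Under per-visit counting, former placebo participants receive active drug at OLE doses 1, 3, 5 and 7 (Section 4.3.2.2, Table 4), so eight visits cover their first four active administrations, mirroring the double-blind rule.

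**The case against.** The strongest reply is that the texts can be reconciled. The footnotes step down to 1 hour at the same visits as the body, and a reduction to 1 hour makes sense only from a longer standard period, evidently 2 hours. A site that observes for exactly 2 hours satisfies both. On this view 'up to' is loose shorthand, and the body states the rule clearly. This stands as evidence of intent, and it is why the footnotes should be brought into line with the body and not the reverse. It does not supply the missing minimum: the footnote still admits any time between 1 and 2 hours.

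A second point is that the body says 'should', while nearby duties use 'must'. That is fair as to force, but the minimum it sets is explicit.

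Third, Table 5 footnote k refers to the pharmacy manual for full details of administration, and that manual may repeat the 2-hour minimum. It was not available for this review. It would not remove a contradiction inside the protocol, and Table 1 footnote s carries no such reference.

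Finally, the practical risk is small: release depends on tolerance, rescue medication must be at hand, and four of the six suggested edits lie outside the affected doses. All of that stands. It limits the importance of the point, and those four edits are conforming only.

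**Conclusion.** The inconsistency is real and the footnotes are wrong as written. It operates in two of them, Table 1 footnote s and Table 5 footnote k, and covers double-blind doses 1 to 4 and OLE doses 1 to 8. The shortfall they permit is less than 1 hour, provided the step-down sentence is read as implying more than 1 hour beforehand; read alone, the words set no lower limit. The 44% OLE share rests on counting doses by visit, as Table 5 does.

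The documents do not show that any site shortened observation, and no estimate, test or sample size depends on this. It should be corrected because it is a live safety instruction and the correction costs almost nothing.

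**What to change.** Bring the Appendix 1 footnotes into line with Sections 4.6.3 and 4.6.4:

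- **Table 1 footnote s and Table 5 footnote k (operative):** replace 'up to 2 hours' with 'a minimum of 2 hours', and 'may be reduced to 1 hour' with 'may be reduced to a minimum of 1 hour'.
- **Table 2 footnote n and Table 6 footnote m (conforming):** make the same two replacements.
- **Table 3 footnote n and Table 4 footnote n (conforming):** change 'about 1 hour' to 'a minimum of 1 hour'.

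The cost is the wording of six footnotes. Visits, data collection and analysis do not change.

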Appendix 1 Schedule of Activities (cont.)

Table 2: Week 36 to the End of Study: 510 mg Q2W

Assessment/Procedure	Treatment Period											Only for Participants Who Have Completed Week 104 when the 12 week study extension is Implemented		Early Term Visit ^a	Unsched Visit
	Final Efficacy and Safety Assessments											Follow-Up Period for Participants Not Enrolling in the OLE			
	Wk 36	Wk 38	Wk 40	Wk 41	Wk 42–50	Wk 52	Wk 54–74	Wk 76	Wk 78–102	Wk 103	Wk 104 ^{a, b}	Wk 116	Wk 152		
Dose number	10	11	12		13–17 _c	18 ^a	19–29 _c	30 ^a	31–43 ^c						
Dose level in milligrams (mg)	510	510	510		510	510	510	510	510						
12-Lead ECG						B		B			x	x		x	x
PK plasma sample ^d				x (Site visit)		B		B		x (Site visit)		x	x	x	x
ADA sample						B		B				x	x	x	x
Clinical RNA sample											x			x	
Serum chemistry ^e and hematology ^f						B		B			x	x	x	x	x
Plasma biomarker sample ^o						B					x			x	x
Complete physical examination (including neurological systems) ^g											x			x	x
Limited physical examination ^h						B		B							x
Weight						x		x			x	x	x	x	x

Appendix 1: Schedule of Activities (cont.)

Table 2: Week 36 to the End of Study: 510 mg Q2W (cont.)

Assessment/Procedure	Treatment Period											Only for Participants Who Have Completed Week 104 when the 12 week study extension is Implemented		Early Term Visit ^a	Unsched Visit
	Final Efficacy and Safety Assessments											Follow-Up Period for Participants Not Enrolling in the OLE			
	Wk 36	Wk 38	Wk 40	Wk 41	Wk 42–50	Wk 52	Wk 54–74	Wk 76	Wk 78–102	Wk 103	Wk 104 ^{a, b}	Wk 116	Wk 152		
Dose number	10	11	12		13–17 ^c	18 ^a	19–29 ^c	30 ^a	31–43 ^c						
Dose level in milligrams (mg)	510	510	510		510	510	510	510	510						
MRI scan ⁱ	B				Wk 48 ^j		Wk 60	B			x ^j			x ^j	x
CSF ^k and matching serum sampling (for participants enrolled based on CSF eligibility criteria only)								x			x			x ^k	
CDR						P&S P		P&S P			P&SP		P&SP	P&SP	P&SP
ADAS-Cog13						P		P			P		P	P	P
Verbal Fluency Task						P		P			P		P	P	P
Coding						P		P			P		P	P	P
ADCS-ADL						SP		SP			SP		SP	SP	SP
FAQ						SP		SP			SP		SP	SP	SP
MMSE						P		P			P		P	P	P
EQ-5D						SP		SP			SP			SP	SP
QoL-AD						P&S P		P&S P			P&SP			P&SP	P&SP
ZCI-AD						SP		SP			SP			SP	SP
RUD-Lite						SP		SP			SP			SP	SP

Appendix 1: Schedule of Activities (cont.)

Table 2: Week 36 to the End of Study: 510 mg Q2W (cont.)

Assessment/Procedure	Treatment Period											Only for Participants Who Have Completed Week 104 when the 12 week study extension is implemented		Early Term Visit ^a	Unsched Visit		
												Final Efficacy and Safety Assessments				Follow-Up Period for Participants Not Enrolling in the OLE	
	Wk 36	Wk 38	Wk 40	Wk 41	Wk 42–50	Wk 52	Wk 54–74	Wk 76	Wk 78–102	Wk 103	Wk 104 ^{a, b}	Wk 116	Wk 152				
Dose number	10	11	12		13–17 ^c	18 ^a	19–29 ^c	30 ^a	31–43 ^c								
Dose level in milligrams (mg)	510	510	510		510	510	510	510	510								
NPI-Q						SP		SP			SP			SP	SP		
C-SSRS BL/SLV						P		P			P			P	P		
Vital signs ^l	B	B	B		B	B	B	B	B		x	x	x	x	x		
Concomitant medications	x	x	x	x	x	x	x	x	x	x	x	x	x	x	x		
Adverse events	x	x	x	x	x	x	x	x	x	x	x	x	x	x	x		
Urine pregnancy test ^m	B	B	B		B	B	B	B	B		x	x		x	x		
Study drug administration ^{d, n}	x	x	x		x	x	x	x	x								

ADAS-Cog13= Alzheimer’s Disease Assessment Scale–Cognition, Subscale 13; ADCS-ADL = Alzheimer Disease Cooperative Study Group–Activities of Daily Living; CDR= Clinical Dementia Rating; CSF = cerebral spinal fluid; C-SSRS=Columbia–Suicide Severity Rating Scale; DTI=diffusion tensor imaging; EQ-5D = EuroQoL-Five Dimensions; FAQ = Functional Activities Questionnaire; FCSRT= Free and Cued Selective Reminding Test; MMSE = Mini-Mental State Examination; MRI = magnetic resonance imaging; NPI-Q= Neuropsychiatric Inventory–Questionnaire; OLE=open-label extension; PET = positron emission tomography; PK = pharmacokinetic; Q2W = every 2 weeks; QoL-AD = Quality of Life–Alzheimer’s Disease; RBR = Research Biosample Repository; RUD-Lite = Resource Utilization in Dementia–Lite; SC = subcutaneous; Unsched = unscheduled; Wk = week; ZCI-AD = Zarit Caregiver Interview–Alzheimer’s Disease.

B = before study drug administration; P = participant completion; P&SP= participant and study partner completion; SP=study partner.

